**Randomization to Stage 1 Treatment.** Eligible participants who provide written informed consent will be randomized in equal proportions to one of three treatments (blocked randomization with random block sizes of 3 and 6 for Stage 1 to obviate any secular trends). Randomization will be stratified by two variables to be tested as moderators (overvaluation of shape/weight (based on  $\geq 4$  EDE item scores) and depression (based on  $> 16$  BDI-II score) ([name], Masheb, Crosby, 2012).

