### DATA ANALYSIS

Baseline demographic and clinical characteristics for randomized groups will be compared using chi-square tests for categorical variables, and ANOVA or Kruskal-Wallis tests for continuous variables. Continuous variables will be examined for adherence to normal distribution using normal probability plots and Kolmogorov-Smirnov tests. If normality not satisfied and transformations do not help with achieving normality, alternative analytic strategies will be considered such as generalized estimating equations or nonparametric methods. Dropouts and completers will be compared. Analyses will be intent-to-treat; patients will be followed regardless of treatment completion to minimize missing data. Primary outcomes will be tested at two-sided 0.05 significance level. Secondary analyses will be adjusted for multiple tests using Bonferroni correction.

Overall Data Analysis Strategy will involve MIXED EFFECTS MODELS (Diggle et al, 2002, Gueorguieva & Krystal, 2004) to compare treatments. These models allow for different numbers of observations per subject, use all available data on each subject, and are unaffected by randomly missing data. Further advantage is capacity to test and account for individual-difference contributions to treatment outcomes (Cudeck, 1996; Cudeck & Klebe, 2002; Hedeker et al., 1996; Hedeker & Gibbons, 1996; Singer, 1998). They provide flexibility in modeling the correlation structure of data. In models for each outcome, we will include fixed effects of time, treatment, and interaction between time and treatment, and random subject-level effects. Because we cannot a priori predict the shape of responses over time in each arm of the trial we will first treat time as a categorical predictor and will then test for polynomial trends over time. We will consider different error structures (e.g., AR1, independence) and select the best fitting one based on information criteria. We will

compare dropout patterns between groups and if there are concerns of informative dropout or informative intermittent missing data, we will use pattern mixture models (Hedeker & Gibbons, 1997) to perform sensitivity analyses.

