(1) **STAGE 1 – Primary Outcomes Aim 1 and Secondary Outcomes Aim 2a:** Compare LDX and CBT effects, alone and in combination, for acute BED outcomes. Analyses examining the co-primary outcomes (reduction in binge-eating and percent weight loss) and examining the secondary outcomes (binge remission, eating disorder psychopathology, depression, metabolic variables) will be intent-to-treat using mixed-effects models per the overall strategy described above. Mixed-model analyses on continuous (or pseudo-continuous) data will use SAS PROC MIXED; mixed-model analyses on binary variables will use SAS PROC GLIMMIX. Logistic regression will be used for categorical outcomes (i.e., remission from binge-eating (defined as 0 binges/past 28 days on EDE interview). Significantly greater reductions in binge eating in CBT and CBT+LDX groups compared to LDX, and weight loss in LDX and CBT+LDX compared to CBT will be considered supportive of our primary aim hypotheses. We do not anticipate significant differences between CBT and CBT+LDX on binge eating and between LDX and CBT+LDX on weight loss but the mixed model approach will allow us to estimate the magnitude of the effects with associated confidence intervals.

(2) **STAGE 1 – Secondary Outcomes Aim 2b:** Explore conceptually and empirically supported predictors, moderators, and mediators for the primary outcomes (reductions in binge-eating and weight loss) and secondary categorical outcome (binge-eating remission). We will use the Kraemer et al (2002) approach to assess predictor, moderator and mediator effects by adding potential predictor, moderator and mediator variables to the models above. Predictors will be identified as variables with significant main effects on the outcome, moderators as variables with significant interactions with treatment on the outcome, and mediators will need to be significantly affected by treatment, to be related to the outcome and have main or interactive effects with treatment on the outcome. We will explore two empirically-supported predictors and moderators of BED outcomes – overvaluation of shape/weight (EDE) and depression (BDI-II) ([name], Masheb et al., 2012; [name] et al., 2013). It is necessary to test previous findings to establish them specifically for CBT and LDX treatments to inform prescription (i.e., for whom these “leading” treatments work best).

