**(5) Secondary Aim:** Generate estimates of cost-effectiveness. We will compute within-study costs for CBT, LDX, CBT+LDX and SMART Stage 2 interventions. Repeated assessments will track additional clinician visits and medication use in our RCT as well as outside treatment contacts through the 18-months. SF-12, administered pre- and post-treatments and at follow-ups, will be used to calculate quality-adjusted life years (QALY) following established methods (Revicki et al., 2005) also used in BED studies of cost-effectiveness specifically of LDX (Agh et al., 2016) and CBTgsh (Lynch et al., 2010; Dickerson et al., 2011), as well as for obesity (Tsai et al., 2005; Malone et al., 2005) including obesity medications (Ara et al., 2012), and for similar SMART designs (switching medication for initial non-responders) in depression (Singh et al 2017). We will calculate incremental cost-effectiveness ratios (ICERs) for the various arms; in these ICERs, the numerator will be the incremental medical cost and the denominator will be the incremental effectiveness of the specific treatment compared to CBT. Confidence intervals for the ICERs will be determined using non-parametric bootstrapping. These ICERs will be compared to the two previous BED (Agh et al., 2016; Lynch et al., 2010) analyses and inform subsequent more definitive larger-scale effectiveness studies.

**POWER ANALYSIS:** We calculated our sample size to have at least 80% power at 2-tailed alpha level 0.025 (adjust for 2 outcomes) to detect clinically meaningful effects in Stage 1 for co-primary outcomes (binge eating and weight loss) and Stage 2 for primary outcome (relapse by initial Responders) at 2-tailed level of 0.05 according based on documented effects of the two treatment components (LDX and CBT). In Stage 1, with 180 subjects total (60 per treatment group), accounting for up to 20% dropout, we can detect medium effect sizes ( $d=0.64$ ,  $f=0.32$ ) for the between group comparisons with more than 80% power at two-sided alpha level of 0.025. These effect sizes are smaller than the effect sizes calculated based on data (Telch et al., 1990; [name] et al., 2005; McElroy et al., 2015, McElroy 2016) which ranged  $d=0.69$  to  $d=0.78$  for the comparison of CBT to LDX on binge-eating and was  $d=1.53$  for LDX vs CBT on percent weight loss. Dropout

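### The Stage 1 alpha of 0.025 covers two outcomes but not the two contrasts within each, and no success rule, order or gate is stated

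*Combined protocol and SAP*

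**What the plan says.** Section 13, Data Analysis, item (1), names "co-primary outcomes (reduction in binge-eating and percent weight loss") and lists what would support the primary hypotheses: "Significantly greater reductions in binge eating in CBT and CBT+LDX groups compared to LDX, and weight loss in LDX and CBT+LDX compared to CBT". This gives four contrasts:

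- Binge eating: CBT vs LDX, and CBT+LDX vs LDX.
- Weight: LDX vs CBT, and CBT+LDX vs CBT.

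The Power Analysis aims for "at least 80% power at 2-tailed alpha level 0.025 (adjust for 2 outcomes"). It then states that d=0.64 (f=0.32) can be detected "for the between group comparisons with more than 80% power at two-sided alpha level of 0.025", "with 180 subjects total (60 per treatment group") and up to 20% dropout. It expects d=0.69 to 0.78 for CBT vs LDX on binge eating and d=1.53 for LDX vs CBT on weight. It gives no effect for either CBT+LDX contrast on these outcomes.

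The opening of Data Analysis has a different alpha: "Primary outcomes will be tested at two-sided 0.05 significance level". On multiplicity it adds: "Secondary analyses will be adjusted for multiple tests using Bonferroni correction". No section adjusts for the contrasts within an outcome, orders them, makes them depend on an overall three-arm test, or says whether one or both must be significant.

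**The concern.** The plan accepts that two primary outcomes need a split of alpha, but it stops there. Within each outcome, two contrasts would each be tested at the full 0.025. What follows depends on a rule that the plan does not give:

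- If either contrast is enough, each outcome has two chances of a false positive and uses more than its 0.025 share.
- If both are needed, error is not inflated, but the power of the rule is lower than the power of one comparison, and only the latter is stated.

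Without a rule, one significant contrast out of two could be read after the fact as support or as failure. This bears on the primary aim of Stage 1. It is also separate from the clash between 0.05 and 0.025, because it remains when 0.025 is used throughout.

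**Working it through.** **Inputs.** From the Power Analysis: 60 per arm, 20% dropout, so 60 × 0.8 = 48 per arm; two-sided alpha 0.025 (critical z = 2.241); d=0.64, 0.69–0.78 and 1.53. From Randomization to Stage 1 Treatment: patients are "randomized in equal proportions to one of three treatments". With equal arms and equal variances, two contrasts sharing a reference arm have covariance σ²/n and variance 2σ²/n each, hence correlation 0.5. The correlation between binge eating and weight is not in the documents; 0 is assumed, with a range to 0.8.

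**1. The plan's own figure.** Power = Φ(d√(n/2) − z). With d=0.64, 0.64 × √24 = 3.135 and 3.135 − 2.241 = 0.894, so power is 81.4%; the noncentral t gives 80.3%. The stated figure reproduces. Also f = 0.64/2 = 0.32 is the two-group relation, so the figure describes one pairwise comparison.

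**2. Error if any contrast counts, all four nulls true.**

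- One outcome: 1 − P(|Z₁| ≤ 2.241, |Z₂| ≤ 2.241; ρ=0.5) = 4.65%.
- Both outcomes, independent: 1 − (1 − 0.0465)² = 9.1%.
- Outcome correlation 0.3, 0.5, 0.8: 8.9%, 8.6%, 7.9%.
- At 0.05 per test: 9.07% per outcome, and 1 − (1 − 0.0907)² = 17.3% over both; 16.9%, 16.4%, 14.9% at the same correlations.

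If the weight effects are real, only the binge contrasts can be false positives, and the error at 0.025 is the one-outcome figure, about 4.6%.

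**3. Power if both contrasts of an outcome are required**, same d for both. Power = Φ₂(d√24 − 2.241, d√24 − 2.241; ρ=0.5).

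- d=0.64: 70.7% (t simulation 69.7%)
- d=0.69: 79.1% (78.3%)
- d=0.78: 90.1% (89.3%)

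For all four contrasts with independent outcomes: 0.707² = 50% if every d=0.64, and about 70.7% if both weight contrasts have d=1.53, where weight power is essentially 100%.

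**4. Fixed sequence with alpha passed on.** Each outcome starts with 0.025 on its first contrast. The second is tested only after the first succeeds, and when both succeed the outcome's 0.025 moves to the other.

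- Error, all nulls true: 1 − 0.975² = 4.9% for independent outcomes, because alpha moves only after a rejection. With real weight effects, the binge chain runs at 0.05 and its error is 5.0%.
- Power, binge d=0.64, both weight contrasts d=1.53: the binge chain runs at 0.05 (z = 1.960). CBT vs LDX: Φ(3.135 − 1.960) = 88.0%. Both contrasts: Φ₂(1.175, 1.175; 0.5) = 80.2%.
- Power if CBT+LDX vs CBT on weight is only d=0.64: alpha is passed on with probability about 0.814. CBT vs LDX: 0.814 × 0.880 + 0.186 × 0.814 = 86.8%. Both: 0.814 × 0.802 + 0.186 × 0.707 = 78.4%.

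Allowing for the t distribution, the ranges are about 86–88% and 78–80%, against about 81% and 70% now.

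**5. Omnibus alternative.** A three-arm test at 0.025 per outcome before the pairwise tests gives 3.9% over both outcomes when all nulls are true (3.4% at outcome correlation 0.8). Once the omnibus null is false, at most one of the three pairwise nulls can be true, so error stays within 2.5% per outcome.

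**The case against.** A reader might infer that the stated 80% power is wrong and that the full Stage 1 hypothesis has 70%. The documents do not support that. The 80% is attached to between-group comparisons and is correct for them; no joint power is claimed. The 70% belongs to both contrasts of one outcome at the minimum detectable effect, not at the larger effects the plan expects. The plan also expects CBT and CBT+LDX to be similar on binge eating, which makes a similar effect for the second contrast reasonable.

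A reader might also infer that the trial will run at nearly twice its intended error. The 9% requires all four nulls to be true, including no LDX effect on weight, where the plan expects d=1.53. With real weight effects the binge error at 0.025 is below 5% overall, though above the 0.025 allotted to that outcome. If both contrasts are required, there is no inflation. Nor are these the only two options, since an omnibus gate would also control error, but none is stated.

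Finally, the study is described as outside the NIH definition of Phase III and is not meant to support a labelling change. The choice of procedure is partly preference.

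These points limit the size of the problem. What stands is that alpha does not cover the tests behind the primary claims and that the rule for success is missing.

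**Conclusion.** The gap is real, moderate in size, and should be fixed. The unstated rule decides which consequence applies: excess false positives if any contrast counts, or a joint power that the plan does not report if both are needed.

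The error figures assume equal variances, 48 per arm and an outcome correlation that the documents do not give. The joint power figures assume the same effect for CBT+LDX vs LDX as for CBT vs LDX. All results at 0.025 presume that the conflict with the 0.05 under Data Analysis is settled in favour of 0.025.

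**What to change.** In Data Analysis, item (1):

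- State whether one or both contrasts are needed for each outcome.
- Reconcile the 0.05 under Data Analysis with the 0.025 in the Power Analysis.
- Name a procedure for the four contrasts. We suggest 0.025 per outcome with a fixed order: for binge eating, CBT vs LDX then CBT+LDX vs LDX; for weight, LDX vs CBT then CBT+LDX vs CBT. Test the second only if the first is significant. Once both contrasts of an outcome are significant, pass its 0.025 to the other outcome.
- An omnibus three-arm test at 0.025 per outcome before the pairwise tests is an acceptable alternative. It needs no order, but it can only remove rejections, so it brings no gain in power.

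In the Power Analysis, give power for one contrast and for both, with the assumed effect for each CBT+LDX contrast.

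The cost is a few sentences and a restated power figure, with no extra patients. Under the fixed order, the second contrast of an outcome cannot be claimed if the first fails. The power gain also depends on both weight contrasts succeeding, and the range above assumes a CBT+LDX vs CBT weight effect between d=0.64 and 1.53, which the documents do not supply.

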#### **Assessment of Treatment Outcome and Time Course.**

Primary Measures: (1) Binge-eating frequency (EDE); (2) weight (measured weight and height and BMI); for Stage 2 LDX vs Placebo test: "Relapse" to DSM-5 threshold of once-weekly binge eating on EDE

Secondary Measures: (1) "remission" (zero binges past 28 days on EDE; eating disorder pathology (EDE global), depression (BDI-II); for exploration of mediators: (2) eating behaviors (EDE, TFEQ, FCI-II), executive control and impulsivity (BIS-11, DDT, Trails) and selected metabolic measures (lipid profiles, HbA1c, blood pressure, HR) to characterize metabolic outcomes and allow comparison with RCTs for LDX and NB.

**Figure 2.** Grid depicting when each measurement is obtained

Assessment Points	BASELINE (2 MTG)	DURING RX STAGE 1 1-MONTH	DURING RX STAGE 1 2-MONTH	POST RX STAGE 1 3-MONTH	DURING RX STAGE 2 4-MONTH	DURING RX STAGE 2 5-MONTH	POST RX STAGE 2 6-MONTH	6 AND 12- MO FOLLOW- UP (18 MONTH TOTAL)
MINI Psychiatric Interview, Height, Credibility,	•							
EDE Interview, SF-12, GPAQ, Lipid Profile, HbA1C, Glucose	•			•			•	•
EDE-Q-I, BDI-II, GLTEQ, Weight, BP, HR	•	•	•	•	•	•	•	•
TFEQ-Restraint	•	•		•			•	•
DDT	•	•		•			•	
FCI-II, PFS	•	•		•	•		•	
BIS-11	•	•		•	•		•	•
ELOCS	•	•		•				
Trails, YFAS, BRS, Amphetamine Testing	•			•			•	
Placebo Ratings					•		•	
Start of New Treatments				•			•	•
Medical History Creatinine w/ EGFR PSQI	•			•				
Adverse Events		•	•	•	•	•	•	
Insulin	•			•				

Liver Function	•			•	• (Non- responde rs only)			
Pregnancy Test	•			•				

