Finally, we expect that “rapid response” will have differential prognostic significance for CBT and LDX. Based on our prior methods ([name] et al., 2006; [name], White, et al., 2012; Masheb & [name], 2007), we hypothesize that overall rapid response will predict superior outcomes in both treatments (i.e., greater weight losses in LDX and greater reductions in binge-eating in both CBT and LDX) and that non-rapid-response will predict no further improvement in LDX but not for CBT (where gradual improvement is expected). In terms of mediators, per Kraemer et al (2002) models, we will explore whether differential symptom changes during treatment are associated with subsequent longer-term primary outcomes (binge-eating and weight loss). Repeated (and early) assessments of eating behaviors and cognitions (EDE-Q-I, TFEQ) constructs relevant to CBT, food-reward constructs (FCI-II, PFS) and executive control (Trails, BIS, DDT) constructs relevant to LDX, food-reward (FCI-II, PFS) constructs relevant to NB, and more general conceptually supported constructs (depression (BDI-II)), will yield relevant change variables for analyses of mediation (i.e., testing subsequent changes in binge-eating and weight). These analyses are exploratory and hence may be underpowered. However, they will provide valuable information in the form of variability estimates and effect size estimates for future more definitive studies.

(3) **STAGE 2 – Primary Aim 1:** Among Responders to Stage 1 treatments with LDX (i.e., LDX and CBT+LDX), compare LDX to placebo as a treatment maintenance strategy. The primary outcome will be “relapse” to DSM-5 level of once-weekly binge-eating and secondary outcomes will be binge-eating frequency, weight loss, eating-disorder pathology, and depression. For the primary outcome (predicting relapse), we will follow

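### The Aim 2b mediator rule makes no adjustment for early change in binge eating or weight, so it can label a by-product of early improvement as a mediator

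*Combined protocol and SAP*

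**What the plan says.** All of this is in the combined protocol and SAP, item 13 (Statistical Considerations), DATA ANALYSIS, unless stated otherwise.

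- **Rule.** Under (2) STAGE 1, Aim 2b, "mediators will need to be significantly affected by treatment, to be related to the outcome and have main or interactive effects with treatment". The plan attributes this to a published approach to mediators and moderators.
- **Model.** Candidates are tested "by adding potential predictor, moderator and mediator variables to the models above". The overall strategy describes those models: "we will include fixed effects of time, treatment, and interaction between time and treatment, and random subject-level effects". No term for early binge eating or early weight is listed.
- **Outcome and time order.** The continuation of Aim 2b says "we will explore whether differential symptom changes during treatment are associated with subsequent longer-term primary outcomes". It adds that the repeated early measures "will yield relevant change variables for analyses of mediation (i.e., testing subsequent changes in binge-eating and weight". The sentence on longer-term outcomes can mean the outcome level, or its change from baseline, at month 3 or later. The sentence on change variables can mean change after the mediator was measured.
- **Status.** "These analyses are exploratory and hence may be underpowered". Aim 2b is listed among the secondary aims. Secondary analyses are to be Bonferroni-corrected, but the number of tests is not given.
- **Data available.** In Figure 2 the row "EDE-Q-I, BDI-II, GLTEQ, Weight, BP, HR" is marked at every assessment, including month 1. TFEQ restraint, DDT, FCI-II, PFS and BIS-11 are also collected at month 1. Trails is not; in Stage 1 it is measured only at baseline and month 3.

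No indirect effect is defined, and no sensitivity analysis for mediator-outcome confounding is described.

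**The concern.** The background (LDX Research Needs) and the Research Plan ask how CBT and LDX achieve their outcomes. Randomisation protects the path from treatment to mediator. It does not protect the path from mediator to outcome. Early binge eating is an obvious common cause of a month-1 craving or mood score and of binge eating at month 3. The plan itself expects early improvement to matter: Aim 2b hypothesises that rapid response predicts better outcome in both treatments. That variable is nevertheless absent from the mediator model.

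At stake is the reading of the mechanism results. A restraint, craving, impulsivity or depression score that only follows early improvement could be reported as a mechanism of CBT or LDX and carried, with its effect size, into the later studies these analyses are meant to inform. No primary conclusion of the trial depends on it.

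**Working it through.** The plan states no figure for mediation, so there is none to reproduce. The check asks how often the rule fires when true mediation is zero.

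**Sample size (item 13, POWER ANALYSIS).** 60 per arm less 20% dropout is 48. For d = 0.64 at two-sided alpha 0.025, power = Φ(0.64 × √(48/2) − 2.241) = Φ(3.135 − 2.241) = Φ(0.894) = 81.4% (80.3% by the t-test). The plan's figure of more than 80% is reproduced, so I use two arms of 48.

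**Model A: early outcome change E, by-product M, later outcome Y.**

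E = d·T + e₁; M = ρE + √(1−ρ²)e₂; Y = sE + √(1−s²)e₃.

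M has no effect on Y. For d I used 0.64 and 0.78, from the power section; applying them to month 1 is an assumption. ρ and s (0.3 to 0.7) are assumptions throughout. Within arm M has variance ρ² + (1−ρ²) = 1, so:

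- the slope of Y on M given treatment is ρs. With ρ = s = 0.5 it is 0.25, although the causal effect is zero;
- given E as well, it is 0;
- the slope of subsequent change (Y−E) on M is ρ(s−1) = 0.5 × (−0.5) = −0.25.

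Share of simulated trials in which M is labelled a mediator (treatment affects M, M correlates with the outcome, and M or M×T is significant beside treatment; alpha 0.05 per test; 4,000 runs):

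| d | ρ | s | Outcome Y | Y, with E as covariate | Outcome Y−E, either sign |
|---|---|---|---|---|---|
| 0.64 | 0.3 | 0.3 | 1.8% | 0.4% | 6.7% |
| 0.64 | 0.5 | 0.5 | 23.8% | 2.6% | 21.8% |
| 0.78 | 0.5 | 0.5 | 32.4% | 3.4% | 31.8% |
| 0.78 | 0.7 | 0.5 | 70.2% | 6.5% | 70.4% |
| 0.78 | 0.7 | 0.7 | 74.4% | 7.7% | 56.0% |

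Hand check of row 2: treatment affected M in 33.8% of runs and M had an effect beside treatment in 69.9%; 0.338 × 0.699 = 23.6%, against 23.8% simulated.

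The last column needs care. Its slope is ρ(s−1), which is negative for any s below 1. A better mediator change goes with less later improvement. That is regression to the mean, not mediation of benefit.

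**Model B: baseline, month 1 and month 3 (b₀, b₁, b₃).**

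b₁ = 0.5b₀ − 0.6·arm + noise; mediator change = λ(b₁−b₀) − δ·arm + noise; b₃ = 0.6b₁ + noise; reliability 0.8.

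All coefficients are assumptions. With change from baseline as outcome:

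| λ | δ | Rule as written | With baseline and month-1 outcome |
|---|---|---|---|
| 0.5 | 0.5 | 67% | 8% |
| 0.3 | 0.5 | 26% | 5% |
| 0.5 | 0 | 18% | 2% |
| 0.3 | 0 | 3% | 0.6% |

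A separate run of the same structure gave 5% to 67% as written and about 1% to 6% adjusted. With the month-3 level as outcome it gave 2% to 18%. With month 3 minus month 1 as outcome, about 1% of trials or fewer fired in the direction mediation requires.

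**What the adjustment costs.** A mediator acting directly on month 3 (effect 0.3 SD) was found in 76% of trials unadjusted and 61% adjusted. A mediator acting only through month-1 binge eating (treatment effect on it 0.8; path 0.3, 0.5, 0.7) was found in 21%, 50% and 75% with the month-3 level as outcome, and in 6%, 8% and 10% after adjustment.

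**The case against.** The best defence has four parts.

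1. **The rule is more than a test of association.** It requires a treatment effect on the mediator and an effect of the mediator in a model that already contains treatment. This stands. A reader who takes the word associated in the later sentence of Aim 2b might infer a bare association test; the stated rule does not support that.

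2. **Time order protects the analysis.** This stands only if the outcome is change after month 1, where labels in the mediating direction nearly vanish. The plan also speaks of longer-term outcomes and does not settle which it means.

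3. **Bonferroni applies.** It lowers the rate without removing the bias. In Model A at 0.005 per test, the rate was 3% for d = 0.64, ρ = s = 0.5 and 41% for d = 0.78, ρ = s = 0.7. Assuming seven mediator measures (0.05/7 = 0.007), Model B with change from baseline fell from 33–50% to 9–23% (λ 0.3, δ 0.5), the ranges reflecting mediator residual SDs of 0.87 and 0.6.

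4. **The work is exploratory.** This limits the consequence. But low power adds noise, whereas this adds bias, and the effect sizes are meant to be reused.

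A reader might also infer that the rule will usually mislabel. Higher rates than 67% can be produced: 74% in Model A, up to 87% in Model B with the smaller mediator residual, and nearly 100% if the planning effect for weight (d = 1.53) is placed at month 1. The documents do not support any of these as an expected rate. They give no correlation, reliability or month-1 effect, and the highest Model B rates arise only with change from baseline as an unadjusted outcome.

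**Conclusion.** The point holds in a limited form. As written, the rule cannot separate a mediator from a by-product of early improvement, because nothing in the model accounts for early binge eating or weight. How often this would mislead is not known: about 2% to 67% in the three-visit simulations with no true mediation, and close to zero in the mediating direction if the outcome is change after month 1. All these figures assume one mediator, two arms, normal variables and correlations that the documents do not give, and they are before any Bonferroni correction.

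A reader might infer that a variable should count as a mediator only if it survives adjustment for the month-1 outcome. That goes too far. Mediator and covariate come from the same visit, so if craving or restraint falls first and reduces binge eating within the month, the covariate lies on the causal path and adjustment removes a real effect. The two models answer different questions, and both are needed.

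**What to change.** In item 13, Aim 2b:

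1. State the mediator outcome: binge eating or weight at month 3 or later, with the baseline value of that outcome as a covariate.
2. For each mediator measured at month 1, fit the model without and with the month-1 level of the same outcome (EDE-Q-I binge frequency, or weight).
3. Report both results side by side. A variable that holds in both is supported as a mediator distinct from early improvement. One that holds only without the adjustment is reported as not distinguishable from either a by-product or a mediator acting through early outcome change.
4. Say how Trails will be handled, since it has no month-1 value and cannot enter these models.

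The cost is a few sentences of plan text and one extra model per mediator, with no new data. The adjusted model loses some power for a mediator acting directly on month 3 (about 76% to 61%) and has little power for one acting entirely through the month-1 outcome. That is why it should sit beside the unadjusted model and not replace it.
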